CoronaVirus Infectious Disease 2019 (COVID-19), since its initial discovery in December 2019 has affected millions of lives across the world. As of this writing it has infected over 3 million people across the world with almost a third of those in the United States (US). It has so far claimed over 200,000 lives worldwide with over a quarter of those in the US.

COVID-19 is caused by Severe Acute Respiratory Syndrome CoronaVirus-2 (SARS-CoV2), a β -coronavirus. It most commonly affects lungs leading to acute respiratory distress syndrome, but involvement of other organs leading to cardiomyopathies, acute kidney injury (AKI) and gastrointestinal systems has been frequently described. AKI, a sudden dysfunction of kidneys, is common among critically ill patients and is associated with high mortality, morbidity and increase in healthcare costs. It is seen in 15-25% patients with COVID-19. The treatment relies on prevention of progression of AKI and management of its complications. Initiation of dialysis therapy is needed in 6-13% of critically ill patients with AKI and is associated with very high mortality. As such there is a critical need to identify and develop therapies to delay the progression of AKI in these patients.

Our overarching goal is to improve the outcomes of critically ill patients with or at risk for development of AKI. The objective of this application is to determine the role of urine alkalinization in prevention of development and progression of AKI in critically ill patients with COVID-19. A recent study has shown invasion of renal tubular epithelial cells by SARS-CoV2 virus. Urinary alkalinization, that has been used in millions of patients to reduce renal toxicity from various nephrotoxins including chemotherapeutic agents and drug overdoses (e.g. aspirin), will lead to a conformational change in the amino acids of the receptor binding domain of coronavirus leading to decreased binding affinity of the virus to its receptor on renal tubular epithelial cells. We hypothesize that alkalinization of urine is safe and effective to prevent development of AKI in patients with COVID-19. To achieve our objective we are proposing to conduct a pragmatic randomized clinical trial of 40 patients testing positive for COVID-19 with the objective of preventing the development of moderate-severe AKI. We have two specific aims.

Aim 1: To determine the feasibility and safety of a pragmatic urine alkalinization protocol for the prevention of AKI in patients testing positive for COVID-19. Primary outcome will be the proportion of patients treated who achieve >50% of urine measurements above pH 7.0 over the duration of intervention. Other outcomes will include protocol adherence and provider acceptance.

Aim 2: To determine the effectiveness of urine alkalinization for prevention of AKI in patients testing positive for COVID-19. Primary outcome will be the number of days alive and free of stage 2-3 AKI (up to 28) in each group. Secondary endpoints will include the proportion of patients developing stage 2-3 AKI (or stage 3 if already at stage 2 at enrollment); ventilator-free days to 28 and hospital-free days to 60.

Completion of this study will provide clinically relevant information regarding the role of urine alkalinization in prevention of AKI associated with COVID-19. This will have wide ranging implications for patients with COVID-19. [name], Professor and Vice Chair for Research in the Department of Critical Care Medicine at the University of Pittsburgh, a co-I on this application and my co-mentor for the WVCTSI research scholar application is also in the process of conducting this study at the University of Pittsburgh. At the completion of this study, the results from both centers (WVU and UPitt) will then be pooled and changes in AKI rates, and survival will be examined among patients with COVID-19.

B. RESEARCH STRATEGY (5 pages max)

1. Background

Severe Acute Respiratory Syndrome Coronavirus 2 (SARS-CoV-2) is rapidly spreading around the world. The current outbreak of infections with SARS-CoV-2 is termed Coronavirus Disease 2019 (COVID-19). Two other coronavirus infections, SARS in 2002-2003 and Middle East Respiratory Syndrome (MERS) in 2012, both caused severe respiratory syndrome in humans. All 3 of these emerging infectious diseases are caused by β -coronaviruses. COVID-19, declared a pandemic by the World Health Organization on Mar 11, 2020, is associated with high mortality in patients admitted to intensive care units (ICUs) [1]. Though COVID-19 primarily affects lungs leading to Acute Respiratory Distress Syndrome (ARDS), other life-threatening acute organ dysfunctions such as acute kidney injury (AKI) and cardiomyopathies are also commonly described.

AKI, defined as a sudden decrease in function and damage to kidneys is common among critically ill patients. The creatinine based Kidney Disease Improving Global Outcomes (KDIGO) criteria define AKI as an increase in serum creatinine by 1.5 times the baseline creatinine of by $\geq 0.3\text{mg/dL}$ [2]. The incidence of AKI at 2.1 per 1000 population is similar to that of heart attacks [3]. It is seen in 10-15% of all hospitalized patients but has been described in over 50% of critically ill patients [4, 5]. It has been described to be present among 15-25% patients with COVID-19 [6, 7].

AKI is not only common but is associated with 3-4 times higher mortality [8, 9], development of chronic kidney disease [10], end stage renal disease [11] and increase in healthcare expenditure [12]. There are no definitive therapies for AKI and treatment primarily rests on prevention of progression of AKI and management of its complications such as hyperkalemia, acidosis and volume overload. Approximately 6-13% of critically ill patients develop severe AKI that requires life-saving dialysis therapy [5, 13] but dialysis itself is associated with high mortality [13] and life-threatening complications such as infections. Therefore there is a great interest in developing therapies and treatment approaches that can prevent AKI in critically ill patients.

2. Hypothesis

We hypothesize that alkalization of urine is safe and effective to prevent development of AKI in patients with COVID-19

3. Significance

Although COVID-19 primarily affects the lungs and may cause severe hypoxemia, other organs including the GI tract, heart and kidney are affected. Acute kidney injury secondary to COVID-19 (COV-AKI) is reported to occur in about 15-25% of patients hospitalized with COVID-19 infection. [6, 7] However, AKI was much more common in non-survivors ($>50\%$). The majority of AKI cases are mild to moderate with renal replacement requirement in about 25% of AKI cases. But with COVID-19 taking the form of a pandemic, this has translated into thousands of patients needing dialysis. There are already reports of hospitals running out of dialysis machines to provide life-saving therapy critical for COVID-19 patients with AKI. As such there is a critical need to identify therapies that can delay the development or progression of AKI in these patients. Although kidney failure appears to occur late in the course, patients may begin to

develop AKI within the first 3 days of hospitalization.[6] Thus, there may be a long window for treatment and prevention of early AKI that may decrease renal failure.

Similar to AKI in other settings,[14] COV-AKI is likely to be of variable etiology. Most patients present with single-organ failure (severe hypoxemia). Thus, remote organ injury, including AKI can simply be a consequence of critical hypoxia. Late cardiac involvement, reported in some series, may also cause cardio-renal syndrome. Furthermore, while typical cases do not appear to cause significant hyperinflammation, a few patients develop a microphage-activation syndrome-like phenotype with cytokine storm and high plasma ferritin. This may be the cause of severe AKI in this subgroup. **However, AKI might also result from direct infection of renal tubule epithelial cells (RTEC).** A variety of epithelial cells express the ACE2 receptor and this receptor is used by β -coronaviruses to enter the cells.[15, 16] An autopsy study of 26 COVID-19 patients recently confirmed the invasion of RTECs by SARS-CoV2 with COVID-19[17].

It is this direct viral involvement of the RTEC that this proposal seeks to address. One relatively obvious solution would be to block the ACE2 receptor pharmacologically and hence prevent the virus from entering the cells. While this could be an attractive therapy, ACE2 activity has been shown to be protective in lung injury[18] and no renal specific ACE2r antagonists are available to study. An alternative approach would be to perturb the ability of the receptor-binding domain (RBD) of β -coronaviruses[15] to bind to its cellular (hACE2) receptor. Changes in pH[19] may cause each amino acid residue in the RBD to assume a slightly different 'microscopic' conformation-dependent pKa value. Conformational change may alter the affinity of the RBD for its receptor and this may not jeopardize the function of the enzyme. The pH-induced potential for minor conformational change and/or steric hindrance[20] is possible due to the bulky phenylalanine residue in position 486 (F486 in h2019-nCoV RBD6) and in positions 442 and 472 (Figure 1).[21]

[figure not shown]

Figure 1. Structure of hACE2 receptor and the SARS-CoV RBD.[22]

4. Innovation

Thus, the innovative idea of simply drinking sodium bicarbonate solutions to induce minor changes in blood pH has been proposed.[21] This idea suffers from two major limitations. First, the pH change required to have significant effect on disrupting the RBD is likely to be too great to safely achieve in blood—a rule of thumb is at least 1 pH unit.[23] Second, even if this could be achieved the expression of ACEr is on the apical (lumen) surface of epithelial cells not the basolateral (plasma) side.[16] However, neither of these are problems for the kidney. Urine pH

is normally 5.5-6.5 (not too dissimilar to alveolar fluid—6.4-6.8[24]) and can be easily and safely manipulated. In fact, urine alkalinization protocols have been used for decades to reduce renal toxicity from various compounds (especially chemotherapy) and are recommended by US and European toxicology societies.[25] Here, the strategy will be deployed not for ion trapping but to inhibit the virus from infecting RTEC. Alkalizing the urine using IV sodium-bicarbonate solution to pH of 7.5 or more can be easily and safely achieved. Acetazolamide can also be added if systemic alkalemia is an issue.[25] An additional advantage of this approach is that it is unlikely to interfere with other interventions that can be studied in these patients (e.g. steroids) which are directed at the lungs.

5. Approach

We will conduct a pragmatic RCT using alkalinization of urine such that most ICU COVID-19 positive patients can be enrolled. Both specific aims will be achieved by the conduct of the trial yet both are independent. The statistical analysis plan for each aim will detail the specific endpoints and hypotheses being testing.

Trial overview: Study inclusion and exclusion criteria are provided in Table 1.

Study design: Open-label randomized trial (1:1) comparing urine alkalinization to standard care. The study will test both feasibility and safety (aim 1) as well as efficacy (aim 2).

Study Management: Study personnel will identify patients and obtain video-enabled informed consent from patients or legally authorized representatives; collect study data and ensure sample collection, processing and storage. The patient's bedside nurse will perform urine pH measurement (dipstick) and deliver the study drug. The study is open-label to facilitate safety and allow for any management of complications (e.g. calcium supplementation).

Table 1. Inclusion/exclusion Criteria

Inclusion Criteria	Exclusion Criteria
Confirmed COVID-19 +	Stage 3 AKI by KDIGO criteria
Admission to ICU or step-down units at WVU	CKD stage 4-5
Foley catheter* and central line (or PICC) in place	Contraindications to Na bicarbonate therapy (e.g. met. alkalosis, severe heart failure)
Age ≥ 18 y	Urine pH > 7.0
	ECMO Patients

*Foley Catheter can be removed 72 hours after enrollment if appropriate documentation of urine output can be maintained

Urine alkalinization may also increase the elimination of certain drugs including hydroxychloroquine. We do not intend to exclude patients taking these drugs but it will be discussed in the consent form and with the treating physicians.

Intervention: The intervention is a modification/simplification of a standard protocol used for decades for the treatment of various drug toxicities (e.g. salicylate) or to mitigate kidney damage from chemotherapy.[25] Simplifications are intended to tailor the intervention to the management of COVID-19 patients and reduce or eliminate any additional staff exposure. We will continue urine alkalinization for 10 days or until patient is discharged from ICU or step-down unit or until the stage 3 AKI or a safety endpoint is reached. Urine pH will be measured at POC by dipstick. The major elements of the interventional protocol are shown in Table 2. Note, much of the monitoring (e.g. blood gases, calcium) is already performed for routine care. The protocol simply ensures that these measurements are timed to maximize patient safety and minimize burden on bedside nurses. The protocol has been developed with input from [name], Professor and Vice Chair for Research in the Department of Critical Care Medicine at the University of Pittsburgh.

Table 2. Protocol highlights
Sodium bicarbonate 225 mmol (225 mL of an 8.4% solution) intravenously over 1h
Recheck urine pH (dipstick) in 2-4 hours (from start of infusion)
Repeat boluses of intravenous sodium bicarbonate to achieve urine pH ≥ 7.2
Monitor urine pH every 2-4 hours until target is reached and then q6-8 hours
Sodium bicarbonate 8.4% solution should not exceed 900 ml (4 boluses) in 24h
Monitor plasma sodium, potassium, calcium every 12 hours and Acid-base status at least every 24 hours (Note: Arterial pH should not be > 7.50 , or venous > 7.55)
Acetazolamide (Diamox) can be administered at physicians' discretion to control systemic alkalinization and to help avoid fluid accumulation.
Avoid fluid accumulation. If urine output does not increase to compensate for the increased fluid (it will in most cases, especially if kidney is protected), Lasix or Diamox can be added.
*If fluid balance cannot be maintained within +1L in 24 hours – protocol will be halted and resumed only if either the fluid balance can be correct to within +500mL in 24 hours or if the primary team decides that the patient has clinically appropriate fluid balance.

Data

collection: Information will be collected about patient demographics – date of birth, age, sex, race, weight, height, co-morbidities including but not limited to diabetes, hypertension, heart failure, coronary artery disease, previous cardiac surgeries, chronic kidney disease, cancers. Given the long history and familiarity with urine alkalinization, potential adverse effects (e.g. metabolic alkalosis, hypocalcemia) are well known. Data about renal function (creatinine, urine output, daily ins and outs), basic metabolic panel, blood gas, home medications, medications given during hospital stay and chart review to identify any relevant complications will also be performed. The provider survey will be performed using an online survey instrument and a link will be emailed to the provider to complete.

Sample collection: We will collect urine samples (1 before, 1 at 24 hours and 1 at 48 hours) from initiation of the protocol. Urine samples will be collected, processed and stored in accordance

with EH&S requirements for COVID-19 samples. At a later date and using alternative funding, we plan to analyze these samples for additional biomarkers either at WVU or at partner institution(s) in that study.[26] These biomarkers measure the cellular stress in the kidney[27] and will be examined in an ancillary study. The samples will be stored initially at the laboratories in WVU and then shipped to partner institution(s) for further testing of urine biomarkers as detailed above.

Statistical analysis: Descriptive statistics will be used for reporting: continuous variables expressed as median and interquartile range while categorical variables as frequency and percentages. No imputation will be performed and missing data will be treated as missing.

Aim 1: To determine feasibility and safety of a pragmatic urine alkalinization protocol for the prevention of AKI

Primary feasibility outcome will be the proportion of patients treated who achieve >50% of urine measurements pH \geq 7.2 over the duration of treatment. Following specific adverse events will be monitored – hypokalemia (K<3.0meq/L), hypocalcemia (Ca<7.6mg/dL when corrected for albumin), Hypernatremia (Na>155meq/L), Volume overload (gaining weight >10% from admission weight during the protocol time-period, need for positive pressure ventilation or intubation due to volume overload), arrhythmias due to hypokalemia or hypocalcemia. To assess safety and feasibility, summary statistics including frequency, mean, standard deviation, median and interquartile range will be provided as applicable. Baseline data will be summarized comparing treatment groups over time. Chi-square/t-test will be used to compare the difference between treatment groups. Mixed model /ANCOVA will be used for repeated measurements over time.

As per the requirements of COE, a Data Safety Monitoring Board (DSMB) has been established that includes [name] [name], [name], [name] and [name] [name]. The DSMB will meet to review any adverse events after 5 and 25 patients have been recruited. In addition, as per the requirements of COE, the DSMB will meet to review any adverse events after the first 5 patients randomized to the interventional drug (open label arm) have been recruited and completed the study.

Aim 2: To determine the efficacy of urine alkalinization for prevention of AKI

Primary efficacy outcome will be the number of days alive and free of stage 2-3 AKI (up to 28) in each group. Secondary endpoints will include the proportion of patients developing stage 2-3 AKI (or stage 3 if already at stage 2 at enrollment); ventilator-free days to 28 and hospital-free days to 60. For AKI-free, ventilator-free, and hospital-free days, zero truncated negative binomial models will be implemented.

Severe AKI will be considered as binary outcome. Multivariable logistic regression will be used to assess the overall odds associated with treatment adjusted by baseline covariates (age, demographics, baseline renal function). Random forest decision tree regression method will be implemented to assess patient variable importance towards the outcome. Hazard will be assessed using cox proportional hazard model.

Sample size determination: The study will be powered to achieve a 50% increase in the number of days alive and free of stage 2-3 AKI to day 28. We hypothesis an increase from 10 +/- 5 days to 15 +/- 5 days. The sample size needed to achieve this difference is 16 patients per group. We plan to enroll 20 patients per group for a total sample size of 40 patients. [name], Professor of Critical Care Medicine at the University of Pittsburgh and a co-investigator on this application is working towards a similar trial at the University of Pittsburgh (see attached letter of

support). The results from both these studies will then be pooled and changes in AKI rates, and survival will be examined.

Relevance to the current COVID-19 pandemic

There are at least four reasons why this study will have an important impact. First, when severe AKI does occur, mortality is very high.[6, 7] Preventing early AKI may reduce severe AKI as the disease progresses. Second, AKI has considerable effects on the immune system reducing a variety of immune functions[28] and hence might contribute to reduced host response. Third, this is unlikely to be the last β-coronavirus outbreak and different strains may cause even more AKI. Finally, the results of this study would provide critical proof of concept data that could be used to design other therapies to reduce viral RBD affinity. For example, alveolar pH could also be manipulated. Showing feasibility with this safe and available strategy could be the first step toward other related efforts.

C. REFERENCES

2. **KDIGO Clinical Practice Guideline for Acute Kidney Injury** [<https://kdigo.org/wp-content/uploads/2016/10/KDIGO-2012-AKI-Guideline-English.pdf>]

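### The plan fixes 12-hourly electrolyte checks for the alkalinization arm only, so a comparison of laboratory adverse events between arms may partly reflect how often each arm is tested

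*Combined protocol and SAP*

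**What the plan says.** The design is described under Approach as "Open-label randomized trial (1:1) comparing urine alkalinization to standard care". The Intervention paragraph states that "The major elements of the interventional protocol are shown in Table 2", and one line of that table reads "Monitor plasma sodium, potassium, calcium every 12 hours". No other part of the document sets a frequency for these tests, and none sets one for controls.

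The Intervention paragraph qualifies this: "Note, much of the monitoring (e.g. blood gases, calcium) is already performed for routine care". It continues: "The protocol simply ensures that these measurements are timed to maximize patient safety and minimize burden on bedside nurses". On duration it says "We will continue urine alkalinization for 10 days or until patient is discharged from ICU or step-down unit", with earlier stopping for stage 3 AKI or a safety endpoint.

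Under Statistical analysis, Aim 1, three of the monitored adverse events are laboratory cut-offs: potassium below 3.0 meq/L, albumin-corrected calcium below 7.6 mg/dL and sodium above 155 meq/L. There is no rule on confirmation, on which draws count, or on the observation window for controls. The same paragraph provides for summary statistics, then "Chi-square/t-test will be used to compare the difference between treatment groups", and a mixed model or ANCOVA for repeated measurements. The general statistical paragraph says missing data are left as missing.

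**The concern.** An electrolyte value past a cut-off becomes an event only if blood is drawn while it is abnormal. With the same underlying risk, a patient sampled more often has more chances to be counted. The plan guarantees a sampling frequency in one arm and says nothing about the other, and nothing in the analysis adjusts for intervals without a test.

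Safety is part of Aim 1, and these three abnormalities are ones that the intervention could plausibly cause. With 20 patients planned per arm, a surplus of one to three patients with an event could change how the safety result reads. If that surplus came from testing frequency, it would count against the treatment without reflecting harm.

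**Working it through.** The documents give no figure for the safety comparison, so there is none to reproduce. The sample size of 16 per group concerns AKI-free days and does not bear on this point.

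**Inputs from the documents**
- Treated arm: one draw every 12 hours for up to 10 days, so at most 2 × 10 = 20 scheduled draws (Table 2; Intervention paragraph).
- Planned enrolment: 20 patients per arm (Sample size determination).

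**Assumptions, not in the documents**
- Controls have one draw per day, so 10 draws over 10 days.
- The chance *p* that a given value is past the limit is the same in both arms. The main case is *p* = 0.02.
- A patient counts as having an event if any drawn value is past the limit. This is the natural reading of bare cut-offs, but the document does not state a counting rule.

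**Independent draws.** P(at least one event in *k* draws) = 1 − (1 − *p*)^*k*. At *p* = 0.02:
- treated: 1 − 0.98^20 = 0.332
- control: 1 − 0.98^10 = 0.183

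That is 20 × 0.332 = 6.6 against 20 × 0.183 = 3.7 patients, with no true difference. At other values of *p* the chances are 9.5% vs 4.9% (0.005), 18.2% vs 9.6% (0.01) and 64% vs 40% (0.05).

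**Correlated draws.** Successive electrolyte values in one patient are not independent. A first-order autoregressive series on a 12-hour grid was simulated, with the same process in both arms. The treated arm was read at all 20 points and controls at every second point. At *p* = 0.02:

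| 12-h correlation | Treated | Control | Excess per 20 patients | Chi-square rejection, 20 vs 20 | Same, if both arms have the control rate |
|---|---|---|---|---|---|
| 0 | 33% | 18% | 3.0 | 19% | 5% |
| 0.5 | 28% | 17% | 2.2 | 13% | 5% |
| 0.8 | 19% | 14% | 1.0 | 7% | 5% |
| 0.9 | 13% | 10% | 0.5 | 5% | 4% |

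The last two columns give the exact rejection rate of the uncorrected chi-square test at a nominal two-sided 5%. Over *p* from 0.01 to 0.05 and correlations from 0 to 0.9, the ratio of treated to control runs from about 1.9 down to 1.2.

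**Shorter stay.** With 5 days instead of 10, the excess at *p* = 0.02 falls to about 0.6 patients per 20 at correlation 0.8 and 0.35 at 0.9.

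**Equal testing.** If both arms are drawn at the same times, the two probabilities are identical and the gap is zero.

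**The case against.** The strongest reply is that the asymmetry may hardly exist. All patients are in an ICU or step-down unit with a central line or PICC, and the protocol says that much of the monitoring is routine and names calcium as an example. This stands as a limit on size. It does not close the gap: the text says much rather than all, gives no frequency, and gives the timing guarantee to the intervention protocol alone.

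Second, the sentence on chi-square and t-tests follows one about baseline data and does not name adverse events. The stated approach to safety is mainly descriptive, the mixed model depends less on the number of draws, and volume overload, arrhythmias and DSMB review also feed the safety assessment. This stands in part. The sentence sits in the safety and feasibility paragraph, and a descriptive table of event counts by arm carries the same asymmetry. It would be too much, however, to say that the whole Aim 1 safety conclusion rests on this comparison.

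Third, the direction is not certain. More frequent testing may lead to correction before a limit is crossed, which would lower the treated-arm count. The simulation ignores this, and the point stands.

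Fourth, restricting the comparison to common draws could hide real harm arising between them. This also stands, and it is why the restricted comparison must not replace the full listing.

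A reader might also infer that creatinine, and so AKI-free days, inherit the same problem. The documents do not support that. Table 2 lists sodium, potassium and calcium but not creatinine, and a shared panel would be conjecture.

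**Conclusion.** As written, the plan allows ascertainment of three laboratory adverse events to differ by arm and does nothing in the analysis to guard against it. If controls are tested less often, the treated arm may show more events by detection alone.

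The size cannot be established from the documents. Under the assumptions of 2% of values past the limit, daily control draws and a full 10 days, the excess runs from about 3 patients per 20 with independent draws to about 0.5 to 1 at correlations of 0.8 to 0.9. The independent case is an upper illustration for *p* = 0.02, not an expected value. With shorter stays or more frequent control testing the excess shrinks, and it is zero under equal testing.

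A reader might go further and conclude that the comparison is biased against treatment. That would need evidence that controls are in fact tested less often, and the documents contain none. The supportable statement is that the comparison is unprotected.

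**What to change.** Amend the Aim 1 analysis text as follows:
- Keep the table of events from all draws, by arm, as the full safety report.
- Add the number of draws per patient-day by arm for sodium, potassium and calcium, so that any difference in testing is visible.
- Make the between-arm comparison of the three laboratory events on a common basis. One example is the first available result per calendar day in both arms, over the same day 1 to day 10 window from randomisation, while the patient is in the ICU or step-down unit.
- Present the all-draw and common-basis results side by side.

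This needs SAP wording only. It requires no extra tests and no change to patient management. The cost is that transient abnormalities between the common draws, including true treatment effects, leave the common-basis comparison, so neither result should be reported alone. A day without any result in a patient still contributes nothing, and the draw counts will show how often that happens. No change to creatinine handling or AKI staging follows from this point.

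### Table 2 sets the venous pH ceiling (7.55) above the arterial one (7.50), so the venous limit is the looser of the two unless venous pH runs at least 0.05 above arterial

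*Combined protocol and SAP*

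**What the plan says.** Table 2 (Protocol highlights) asks for "Acid-base status at least every 24 hours" and adds the note "Arterial pH should not be > 7.50 , or venous > 7.55". It does not say which sample type to use or what to do when a ceiling is passed.

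The related text is as follows:

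- **Dose.** Boluses of 225 mmol (225 mL) are repeated to reach a urine pH of at least 7.2, subject to a daily limit: "Sodium bicarbonate 8.4% solution should not exceed 900 ml (4 boluses) in 24h". Section 5 (Approach, Intervention) allows treatment for up to 10 days.
- **Response to alkalemia.** Section 4 (Innovation) says "Acetazolamide can also be added if systemic alkalemia is an issue", and Table 2 says "Acetazolamide (Diamox) can be administered at physicians' discretion to control systemic alkalinization". Neither gives a pH at which to consider it.
- **Known harm.** The data collection paragraph says "potential adverse effects (e.g. metabolic alkalosis, hypocalcemia) are well known".
- **Access.** Table 1 requires "Foley catheter* and central line (or PICC) in place". It does not require an arterial line, and step-down patients are eligible.

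**The concern.** Separate limits for arterial and venous samples are reasonable. The problem is the direction of the difference. Two ceilings for one safety concept should mark the same state of the patient, and these do so only if venous blood is the more alkaline by 0.05. Nothing in the documents says so. As written, two equally alkalemic patients could be judged differently because of the sample drawn.

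The study drug raises blood pH, and safety is part of Aim 1. The adverse events specified under Aim 1 carry numeric limits for potassium, calcium, sodium and weight gain, but none for pH or alkalosis. The Table 2 note is therefore the only number a clinician has when deciding on acetazolamide or the next bolus. With an acid-base check required only once in 24 hours, the full daily cap of 4 × 225 = 900 mL could be given between two required checks, although that is a cap and not the expected dose.

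**Working it through.** **Inputs**

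- Arterial ceiling A = 7.50 and venous ceiling V = 7.55, both from Table 2.
- Offset d = venous pH minus arterial pH. The documents do not give it. I assume a range of 0 to -0.05 and also show +0.05, the value at which the two ceilings agree.

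The plan derives no figure from these limits, so there is no published result to reproduce. The stated difference is V - A = 7.55 - 7.50 = 0.05.

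**Formulas**

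- Arterial equivalent of the venous ceiling = V - d = 7.55 - d
- Gap to the arterial ceiling = (7.55 - d) - 7.50 = 0.05 - d
- Venous limit that matches arterial 7.50 = 7.50 + d
- Hydrogen ion concentration in nmol/L = 10^(9 - pH), which at pH 7.50 is 31.6
- Reduction in [H+] relative to pH 7.50 = 1 - 10^(-gap)

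**Results**

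| d | Arterial equivalent of venous 7.55 | Gap | [H+], nmol/L | Reduction | Matching venous limit |
|---|---|---|---|---|---|
| +0.05 | 7.50 | 0.00 | 31.6 | 0% | 7.55 |
| 0 | 7.55 | 0.05 | 28.2 | 10.9% | 7.50 |
| -0.03 | 7.58 | 0.08 | 26.3 | 16.8% | 7.47 |
| -0.05 | 7.60 | 0.10 | 25.1 | 20.6% | 7.45 |

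The gap 0.05 - d is positive for every d below +0.05. The finding that the venous limit is looser therefore does not need the assumed range. It needs only that venous pH does not exceed arterial pH by 0.05 or more. The range sets the size of the gap.

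**Effect of a common ceiling of 7.50.** The residual gap is 7.50 - d - 7.50 = -d, which is 0, 0.03 and 0.05 at d = 0, -0.03 and -0.05. The corresponding gaps now are 0.05, 0.08 and 0.10.

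**The case against.** The strongest objection is that the documents contain no arterial-venous offset, so the sign of d is supplied from outside, and the assumed range leaves out the one value that reconciles the ceilings. It is true that the size of the gap rests on an assumption. The direction needs much less: the venous limit is looser at d = 0 and at any d below +0.05. Only an unstated positive offset of at least 0.05 would remove the problem.

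Other objections limit the reach of the point, and they stand:

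- **No mandated action.** The text does not say that passing a ceiling is a safety endpoint, and acetazolamide is discretionary. Correcting the number would still leave no required response. The note is nonetheless worded as a limit, and there is no other pH figure to guide that discretion.
- **Narrow use.** Any arterial sample is held to 7.50, so the venous figure matters only when a venous sample alone is taken. The access criteria make this possible, but its frequency is unknown.
- **A summary table.** Fuller bedside instructions may exist elsewhere, and the documents do not show whether the two figures were transposed, mistyped or intended.
- **No harm estimate.** The [H+] reductions restate the pH gap on another scale. They do not estimate clinical harm.
- **Other safeguards.** These are the metabolic alkalosis exclusion, titration to urine pH, the 900 mL cap, 12-hourly electrolytes, the halt when fluid balance cannot be held within +1 L, and DSMB review. They reduce the practical risk, but none sets a blood pH value.

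**Conclusion.** The concern holds. The venous ceiling is looser than the arterial one by 0.05 if the two samples have equal pH, and by up to 0.10 if venous pH is 0.05 lower. Over that assumed range it permits an arterial-equivalent pH of 7.55 to 7.60 against the protocol's own 7.50.

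This is a minor bedside safety threshold in the alkalinization arm, but it should be corrected because it is the only blood pH limit given for an alkalinizing drug. Confidence is medium: the offset is assumed, the use of venous-only samples is unknown, and the reason for 7.55 cannot be seen. Endpoints, sample size and analysis are not affected.

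**What to change.** Set the venous limit in Table 2 no higher than 7.50. Preferably, have the investigator state the venous-minus-arterial offset and set the limit at 7.50 plus that offset, which gives 7.45 to 7.50 over the range assumed here.

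At minimum, apply one ceiling of 7.50 to both sample types. This removes the reversed direction but is exactly equivalent only at zero offset. If 7.55 is intended, give the reason in Table 2.

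The cost is one corrected line, with no new tests or visits. Where clinicians act on the number, some patients monitored by venous gas may receive acetazolamide slightly earlier or have a bolus held. That could modestly lower their share of urine readings at target, which feeds the Aim 1 feasibility outcome.
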